5	Death between adequate assessment*	Date of death	PFS Event
6	Death or progression after more than one missed visit/tumor assessment**	Date of last adequate radiologic assessment before missed tumor assessments	Censored

Note:
 
* Adequate tumor assessment is radiologic assessment at regular interval as defined in the protocol.
 
** More than 1 missed visit/adequate tumor assessment of subjects is defined as having the duration between the last adequate tumor assessment and PD or death being longer than 125 days in Treatment Phase of Phase 2 and longer than 181 days in Extension Phase for both Phase I and II.
			

If a subject had PFS event (#1, #4 or #5), the earliest event date will be used.

The priority of the censoring rules is described as follows:

- If a subject missed two or more tumor assessments before PD or death (#6), the subject will be censored at the date of the last adequate tumor assessment before the missed tumor assessments.
Note that if a subject is censored by both this criterion and start of new anticancer therapy criterion, the earliest censoring date will be used.
- If a subject did not have PD or death, the censoring date will be the earliest censoring date if the subject met multiple censoring criteria (#2, #3, #6).

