8 DEFINITIONS AND CONVENTIONS FOR DATA HANDLING

8.1 Visit Windows

Visit windows will be defined to be upper and lower bounds of 1 day of the scheduled visit, following the protocol, which states that efforts should be made to conduct laboratory assessments and administer treatment on the day scheduled (± 1 day).

In Phase 1, tumor assessments for efficacy analysis are to be performed at Week 4 during Treatment Phase, and at Week 12, Week 24 and every 12 weeks thereafter or as clinically indicated in the Extension Phase. In Phase 2, tumor assessments for efficacy analysis are to be performed at Week 8 and Week 16 during Treatment Phase, and at Week 24 and every 12 weeks thereafter or as clinically indicated in the Extension Phase. All responses are to be confirmed at a follow-up examination after ≥ 28 days following the initial indication of response. Efforts should be made to conduct tumor assessments on the day scheduled (± 7 days).

In the calculation of descriptive statistics for laboratory values and vital signs, if a visit has multiple observations, the observation closest in date and time to the target visit day will be used in the analysis. If 2 or more observations have the same distance to the target visit day, the one that has the highest CTCAE grade or is farthest outside the normal range will be used. The purpose of this windowing is to provide a single record per subject per visit for the calculation of descriptive statistics and change from Baseline per visit. Other safety analyses (e.g., worst grade for laboratory results) will include all observations. All by-visit analyses will be performed using assessments at corresponding scheduled visits recorded in the eCRF. Data from all postbaseline assessments including those at scheduled and unscheduled visits will be used in the shift tables.

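### The DOR missed-scan limits contradict the SAP's own two-missed-scans rule where the Phase 2 scan interval changes after Week 24, and the SAP does not say which date sets the phase

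*SAP*

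**What the plan says.** Row 6 of SAP Table 3 (Section 5.4.2) covers "Death or progression after more than one missed visit/tumor assessment" and censors at the last adequate scan before the gap. The priority text under the table says the same thing as a count: "If a subject missed two or more tumor assessments before PD or death (#6), the subject will be censored".

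The double-asterisk note to the table then defines more than one missed assessment as a gap between the last adequate scan and progression or death "being longer than 125 days in Treatment Phase of Phase 2 and longer than 181 days in Extension Phase", the latter limit serving both study phases. The single-asterisk note adds: "Adequate tumor assessment is radiologic assessment at regular interval as defined in the protocol".

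SAP Section 8.1 has Phase 2 scans "performed at Week 8 and Week 16 during Treatment Phase, and at Week 24 and every 12 weeks thereafter", with a window of 7 days either side. In Phase 1 they are "performed at Week 4 during Treatment Phase, and at Week 12, Week 24 and every 12 weeks thereafter". SAP Section 3.2 gives the Phase 2 Treatment Phase as 4 cycles, or 16 weeks.

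**The concern.** Row 6 and the priority text count missed scans. The note counts days. The two agree only if the day limit matches the scan interval that applies after the last scan, and in Phase 2 that interval changes from 8 to 12 weeks at Week 24. The stretch Week 16, 24, 36 mixes the two, and neither limit is built for it.

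The stretch matters for DOR. A response seen at Week 8 and confirmed at Week 16 has Week 16 as its last Treatment Phase scan, so the gap to any later event starts where the limits fit worst. What is at stake is whether such an event is counted or censored, and whether two programmers working from the same SAP would reach the same answer.

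**Working it through.** **Inputs.** Limits: 125 and 181 days (Table 3 note). Phase 2 scans: Weeks 8, 16, 24, 36, 48 and so on, each within 7 days either way (SAP 8.1). Treatment Phase: 16 × 7 = 112 days (SAP 3.2).

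**1. Reproduce the limits.** Two intervals, plus 7 days at each end, less one day:
- 8-week interval: 2 × 56 + 14 − 1 = 125.
- 12-week interval: 2 × 84 + 14 − 1 = 181.

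Both match exactly, so each limit presumes two equal intervals in a row.

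**2. Gap when exactly one scan is missed and progression is found at the next scheduled scan.**

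| Last scan | Missed | Progression at | Nominal gap (days) | Range with windows |
|---|---|---|---|---|
| Week 8 | Week 16 | Week 24 | 16 × 7 = 112 | 98 to 126 |
| Week 16 | Week 24 | Week 36 | 20 × 7 = 140 | 126 to 154 |
| Week 24 | Week 36 | Week 48 | 24 × 7 = 168 | 154 to 182 |

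**3. Reading A: the phase is that of the last adequate scan.** Section 8.1 places the Week 16 scan in the Treatment Phase, so 125 days applies to the middle row. The smallest possible gap has Week 16 done 7 days late and Week 36 done 7 days early: (252 − 7) − (112 + 7) = 126, which is more than 125. All 15 × 15 = 225 combinations of window shifts exceed the limit. This event after one missed scan is therefore always censored, against row 6 and the two-or-more rule.

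**4. Reading B: the phase is that of the event.**
- An event in the Treatment Phase falls by Day 112, or by Day 119 if it is found at a Week 16 scan done a week late. The earliest Week 8 scan is Day 49. The longest gap is 119 − 49 = 70 days, so a responder can never reach 125.
- Later events take 181 days. The Week 16-to-36 progression in step 3 is now counted correctly (0 of 225 combinations are censored).
- If Weeks 24 and 36 are both missed after a Week 16 scan done on its nominal day, the Week 36 window closes at 36 × 7 + 7 − 112 = 147 days. A death or unscheduled progression at 148 to 181 days (34 days) is counted as an event although two scans were missed.

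**5. Constant stretches.** In the first and third rows of the table, one missed scan is wrongly censored only at the extreme gap of 126 or 182 days, 1 of 225 combinations each. In the other direction, after a nominal Week 24 scan with Weeks 36 and 48 missed, the second window closes at 48 × 7 + 7 − 168 = 175 days. Events at 176 to 181 days (6 days) are then counted; if the Week 24 scan was a week late, this becomes 13 days.

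**The case against.** The limits are not arbitrary. They follow from the 8- and 12-week intervals and the windows, and they do their job wherever the interval is constant. A reader might infer that they are out of line with the schedule throughout; steps 1 and 5 show that they are not.

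A reader might also infer that both errors occur together. They belong to alternative readings. Always censoring the one-miss case needs Reading A; a wide band of two-miss events counted needs Reading B. Reading A is the more plausible, because Reading B leaves the 125-day limit without use for a responder. SAP Section 9 puts derivation rules in separate documents, which may settle the choice. Settling it would still not bring the note into line with row 6, since each reading fails at the interval change.

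DOR includes confirmed responders only, and confirmation needs a second scan at least 28 days later. A response first seen at Week 16 with no further scan until progression never enters DOR. This narrows the case mainly to a Week 8 response confirmed at Week 16. A Week 16 response confirmed at an unscheduled scan may also be caught, since the single-asterisk note, read literally, would not accept that scan as adequate. The same reasoning leaves little to fix in Phase 1: the note gives no limit for a last scan at Week 4, but one post-baseline scan cannot confirm a response.

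It is tempting to say that DOR is lengthened. That does not follow. Censoring removes an event but also shrinks the risk set for the events in between. With assumed DORs of 10, 16, 20, 28 and 52 weeks, the Kaplan-Meier median is 20. Take the 28-week patient as responding at Week 8 and progressing at Week 36, and censor that patient at Week 16, that is, at 8 weeks of DOR. Survival then steps to 0.75, 0.50 and 0.25 at 10, 16 and 20 weeks, and the median becomes 16 (18 by the midpoint convention).

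**Conclusion.** The note gives a result that contradicts the rule it is meant to apply. The fault is confined to the change of interval over Weeks 16, 24 and 36 in Phase 2, together with the unstated date that sets the phase. On the last-scan reading the error is certain whenever the pattern occurs; on the event-date reading it affects a 34-day band after a nominal Week 16 scan.

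The documents give no rate of missed scans, so the frequency is unknown. If the pattern occurs once, its weight depends on the number of responders. At the target rate, 25% of 20 is 5, so one event is 1/5 of the DOR data. At the smallest count that is not declared a failure (3 of 20), it is 1/3.

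DOR is secondary and enters no go/no-go rule. ORR at Week 16 and the two-stage decisions are unaffected. The correction is worth making because the rule is wrong as written and cheap to put right, not because the trial's main conclusion depends on it.

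**What to change.** Replace the day limits in the double-asterisk note with a direct count. Row 6 would apply when two or more scheduled scan windows (scheduled week, 7 days either side) have closed without an adequate scan between the last adequate scan and the progression or death. This matches the two-or-more rule already in the SAP and needs no phase.

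If day limits are kept, state that the phase is that of the last adequate scan, and use more than 154 days (140 + 14) when that scan is Week 16 in Phase 2. A few window-edge cases would remain: after a nominal Week 16 scan with Weeks 24 and 36 missed, a death at 148 to 154 days would still be counted.

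The cost is one change to the SAP wording and one programming rule. No new data are needed.

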5.4.3 Exploratory Efficacy Analyses

5.4.3.1 Biomarkers, Archival Tumor Tissue, Lenvatinib Exposure and AEs of Special Interest

- To evaluate blood, tumor, and safety (eg, hypertension) markers as correlative biomarkers of treatment effects and outcomes of lenvatinib in combination with everolimus.
- To assess candidate alterations in genes and/or proteins that may contribute to tumor development and serve as predictive markers of response in archival tumor tissue from pediatric subjects.
- To explore relationships between lenvatinib exposure and safety (eg, adverse events [AEs] of special interest).

A separate analysis plan will be developed for these analyses.

5.4.3.2 Other Exploratory Efficacy Analyses

- Graphical displays will be prepared for the maximum tumor shrinkage in target lesions, defined as the maximum percentage change from Baseline in the sum of the diameters of the target lesions at data cutoff.

5.5 Pharmacokinetic, Pharmacodynamic, Pharmacogenomic, and Other Biomarker Analyses

5.5.1 Pharmacokinetic Analysis

Lenvatinib and everolimus concentration versus time data will be tabulated and summarized and graphically presented (Box and Whisker plots).

Plasma concentrations of lenvatinib from the intense sampling in Phase 1 will be used to determine the following PK parameters for Cycle 1, Day 1 and Cycle 1, Day 15: area under the plasma concentration time course profile (AUC_{0-t}), maximum observed concentration (C_{max}), time from drug administration to the maximum observed concentration (T_{max}). Other PK parameters (AUC_{0-inf} , half-life [$t_{1/2}$], clearance [CL/F], and volume of distribution [V_Z/F]) may be determined as data permit. The following graphical displays will be prepared:

- Trellis plots of plasma concentrations at Cycle 1, Day 1 and Cycle 1, Day 15
- Mean and SD of lenvatinib plasma concentration by planned dose level group over time (Cycle 1, Day 1 and Cycle 1, Day 15)
- Box and Whisker plots of PK parameters by planned dose level group at Cycle 1, Day 1 and Cycle 1, Day 15

For both lenvatinib and everolimus, data from Phase 1 and 2 of the study will be pooled with available data from other studies and subjected to population PK analysis. For each drug, the PK model will be parameterized in terms of clearance and volume of distribution. Details of the population PK analysis will not be included in the study SAP and will be provided in a separate analysis plan.

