9.4.1.1 Study Treatment Dose Reduction and Interruption Instructions

Dose reduction and interruptions for subjects who experience lenvatinib-everolimus combination therapy-related toxicity will be managed as described in [Table 5](#). Investigators will decide the probability of the event being related to protocol therapy as to whether dose modification of drug therapy is required.

Doses in the Dose Adjustment column are based on a presumed starting dose of 11 mg/m² lenvatinib and 3 mg/m² everolimus. Dose reductions will occur in succession based on the previous dose level. Each dose level reduction due to toxicity at a given BSA is

approximately 25% reduction from the previous dose. Once the study drug dose has been reduced, it may not be increased at a later date, unless the dose was mistakenly decreased; in this situation, the sponsor's approval is required to increase the dose.

Asymptomatic laboratory abnormalities, including Grade ≥ 3 abnormalities (eg, elevations of amylase and lipase) that are not considered clinically relevant by the investigator, should be managed per institutional guidelines; continuation of treatment should be discussed with the sponsor.

Table 5 Dose Modification Guidelines for Lenvatinib-Everolimus Combination Treatment-Related Toxicity

Treatment-Related Toxicity ^{a,b}	Management	Dose Adjustment
Grade 1 or Tolerable Grade 2		
	Continue treatment	No change
Intolerable Grade 2^{c, d, e} or Grade 3^f		
First occurrence	Interrupt lenvatinib and everolimus until resolved to Grade 0-1 or tolerable Grade 2	Reduce lenvatinib dose to 8 mg/m ² (or approximately 25% reduction of the starting dose) orally once a day (one-level reduction) and resume everolimus at the same dose as prior to dose interruption
Second occurrence (same toxicity or new toxicity)	Interrupt lenvatinib and everolimus until resolved to Grade 0-1 or tolerable Grade 2	Reduce lenvatinib dose to 6 mg/m ² (or approximately 25% reduction from the previous dose level) once a day (one-level reduction). Dose reduction of everolimus to 3 mg/m ² every other day may be considered for Grade 3 toxicity ^e

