9.4.5 Selection and Timing of Dose for Each Subject

Lenvatinib and everolimus are to be administered orally once a day at approximately the same time without regard to food intake for 28 days from Cycle 1 onward. If a subject misses a dose of lenvatinib, it may be taken within the 12 hours following the usual time of the dose. If more than 12 hours have elapsed from the time of the usual daily dose, lenvatinib should be taken the next day at the usual time. In the event a subject vomits after study drug administration, the subject should not take another dose until the next scheduled dose.

Refer to everolimus prescribing information for recommended everolimus dosing information.

Study drugs should be administered at the clinic on PK sampling days. All scheduled visits must be conducted as per protocol, irrespective of treatment interruption. If holidays or personal schedules make administration impossible on the scheduled days, then administration should be resumed as soon as possible.

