5.2 Study Subjects

5.2.1 Definitions of Analysis Sets

The following analysis sets will be defined:

- **Evaluable Analysis Set**, defined as all evaluable subjects, who have measurable disease present at baseline and at least 1 postbaseline efficacy assessment, unless they have discontinued prior to the first efficacy assessment due to progressive disease. Efficacy analyses in Phase 2 will primarily be based on the Evaluable Analysis Set.
- **Safety Analysis Set**, defined as all subjects who received at least 1 dose of study drug (lenvatinib or everolimus). This will be the analysis set for disposition, demographic and baseline characteristics, previous anticancer medications, prior and concomitant medications, procedures and radiotherapy, medical history, efficacy analysis in Phase 1 as well as all safety evaluations.
- **Pharmacokinetic (PK) Analysis Set**, defined as subjects in the Safety Analysis Set who had at least 1 measurable postdose plasma concentration with an adequately documented drug administration history.
- **Pharmacodynamic Analysis Set**, defined as all subjects in Safety Analysis Set who had evaluable pharmacodynamic data.

All analyses will be presented by planned dose level group in Phase 1 and separately for each study cohort in Phase 2, unless otherwise specified. A summary table and listing will also be provided to identify subjects in each analysis set.

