5.3.6 Other Considerations

5.3.6.1 BSA Dose Adjustment and Dose Capping

Subjects in Phase 1 will receive study drug as described in Protocol Section 9.1, Tables 3 (lenvatinib) and 4 (everolimus).

The actual dose level of lenvatinib and everolimus could be different from the planned dose level due to the adjustment of BSA and dose capping. The actual dose level of lenvatinib and everolimus will be calculated from actual daily dose and BSA. The subject with dose capping will be listed. For Phase 1 and Phase 2 the planned dose level will be used for column grouping across all analyses.

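### Day 15 lenvatinib PK in Phase 1 is summarised by planned dose level only, so a subject held and then reduced lowers the exposure reported for that level

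*SAP*

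**What the plan says.** SAP 5.5.1 derives AUC0-t, Cmax and Tmax for lenvatinib from the intensive Phase 1 sampling on Cycle 1 Day 1 and Cycle 1 Day 15. It plots mean and SD concentrations by planned dose level on both days, and adds "Box and Whisker plots of PK parameters by planned dose level group at Cycle 1, Day 1 and Cycle 1, Day 15".

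SAP 5.3.6.1 makes this general: "For Phase 1 and Phase 2 the planned dose level will be used for column grouping across all analyses". The same section states that "The actual dose level of lenvatinib and everolimus will be calculated from actual daily dose and BSA", but it attributes differences between actual and planned dose to BSA adjustment and capping. Toxicity reductions are not mentioned there, and the calculated actual dose is not used for grouping.

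The PK Analysis Set (SAP 5.2.1) takes subjects from the Safety Analysis Set "who had at least 1 measurable postdose plasma concentration with an adequately documented drug administration history". It sets no condition on the dose at a given visit.

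In the protocol, Table 5 (section 9.4.1.1) handles a first intolerable Grade 2 or Grade 3 event as "Interrupt lenvatinib and everolimus until resolved to Grade 0-1 or tolerable Grade 2", after which lenvatinib goes from 11 to 8 mg/m2. Section 9.4.5 adds: "All scheduled visits must be conducted as per protocol, irrespective of treatment interruption". Section 9.5.1.4.1 and footnote n of Table 7 ask only that the sponsor be contacted if an interruption falls on a PK time point.

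**The concern.** A Day 1 sample is enough to place a subject in the PK Analysis Set. If that subject is then held and restarted at a lower dose before Day 15, the Day 15 profile reflects the lower dose and incomplete re-accumulation, yet it is counted at the planned level. Compared with the same subjects on the assigned dose, the shift can only be downward.

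The plan foresees this sequence elsewhere. SAP 5.6.1.3 uses 11, then 0, then 8 mg/m2 as its worked example of a dose reduction, and the DLT definition includes a Cycle 1 interruption or reduction that brings dosing below 75% of plan. The PK section does not carry this through.

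At stake is the description of exposure at each Phase 1 dose level. PK characterisation is a secondary objective, and Day 15 is the only intensively sampled day after repeated dosing. Cohorts are small (two to six concurrent subjects), so one subject has visible weight.

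**Working it through.** The plan states no figure to reproduce, so this is an illustration of size.

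**Inputs**
- Half-life: Protocol 9.4.7 equates one week with five half-lives before major surgery, so 168 h / 5 = 33.6 h. This is an assumption taken from a washout rule, not a PK estimate.
- Dose before and after a first event: 11 and 8 mg/m2 (Table 5).
- Further assumptions: one compartment, linear PK, doses treated as boluses, and 8 mg/m2 taken on Day 15.
- Group size: six, as in Table 2 of the protocol.

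**Formula**
The fraction left after one day is r = 2^(-24/33.6) = 0.6095. The amount carried into Day 15 is A = sum over Days 1-14 of dose x r^(15 - day). Postdose exposure relative to uninterrupted dosing is (A + Day 15 dose) / (A_full + 11).

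**Uninterrupted 11 mg/m2**
A_full = 11 x 1.5593 = 17.15, and the denominator is 17.15 + 11 = 28.15.

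**Hold-then-reduce cases**

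| Case | A | Relative postdose exposure | Fall in mean, 1 of 6 |
|---|---|---|---|
| Held Days 8-10, then 8 mg/m2 | 11.28 | 19.28 / 28.15 = 0.685 | 0.315 / 6 = 5.3% |
| Held Days 8-12, then 8 mg/m2 | 8.37 | 16.37 / 28.15 = 0.581 | 0.419 / 6 = 7.0% |
| Held Days 10-14, 8 mg/m2 on Day 15 (extreme) | 1.43 | 9.43 / 28.15 = 0.335 | 0.665 / 6 = 11.1% |

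**Sensitivity**
With a 24 h half-life (r = 0.5) the ratios are 0.708, 0.640 and 0.379, and the falls are 4.9%, 6.0% and 10.3%.

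**Scale**
The step from Dose Level 1 to Dose Level 2 is 14/11 - 1 = 27.3%.

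**Would dose-normalising be enough?**
Multiplying the ratios by 11/8 gives 0.94, 0.80 and 0.46. Dividing by the Day 15 dose therefore corrects a stable reduction but not a recent hold, so a flag is needed as well.

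**How many such subjects can a level contain?**
If 8 mg/m2 continues to Day 28, Cycle 1 dosing as a share of 28 x 11 = 308 is:
- first case: (77 + 32 + 112) / 308 = 71.8%
- second case: (77 + 16 + 112) / 308 = 66.6%
- third case: (99 + 0 + 112) / 308 = 68.5%

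All are below 75%, so each is itself a DLT. Two in six would mean the level exceeds the MTD, unless the conditional expansion to 12 applies.

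**The case against.** The strongest reply is that little depends on these displays. They are descriptive. Protocol 9.1 bases the MTD/RP2D on DLTs and on review of safety and clinical data. The dose-level displays rest on intensive Phase 1 sampling, while Phase 2 uses sparse samples and population PK under a separate plan. Trellis plots, dose administration listings and DLT listings with dosage would let a reader find affected subjects, and CL/F may be derived as data permit. Dataset specifications and table shells are separate documents and may contain a rule. All of this limits the consequence. None of it changes the by-level summary as the SAP states it.

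A reader might also infer a much larger effect from predose levels, or from two affected subjects in six or one in three. The documents do not support that:
- The displayed parameters are AUC0-t, Cmax and Tmax, not troughs.
- Footnote n requires predose samples after Day 1 to be drawn 24 h after the previous day's dose, which a subject held up to Day 14 cannot provide.
- An interruption on the sampling day goes to the sponsor.
- Under Table 2, one DLT in three keeps enrolment at that level, and two in six normally lead to de-escalation.

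Finally, restricting the summary to subjects on full dose would select those who tolerate the level. If toxicity follows exposure, that too lowers the reported value. This stands, and it is why restriction alone is not the remedy.

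**Conclusion.** The gap is real and modest. As written, the SAP pools Day 15 profiles from held or reduced subjects with those on the assigned dose, and the two documents contain no correcting rule. One such subject in six lowers the level's mean postdose exposure by about 5-7%, or 11% in the extreme case, against a planned step of 27%. These figures rest on the 33.6 h half-life, linear one-compartment behaviour, the chosen hold dates and a dose of 8 mg/m2 on Day 15. The effect needs at least one affected subject, and the documents give no count. It would be wrong to infer that dose selection or any error rate is affected. The point concerns only how Phase 1 exposure by level is described.

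**What to change.** In SAP 5.5.1, exempt Day 15 PK from the planned-level-only rule of 5.3.6.1:

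1. Alongside the by-level displays, present Cmax and AUC0-t normalised to the actual mg/m2 dose, which 5.3.6.1 already calculates.
2. From the dosing records, flag any subject whose dose was below the assigned dose or interrupted in the 7 days before the sample (five half-lives on the protocol's own equivalence). Count a capped or BSA-adjusted nomogram dose as the assigned dose.
3. Show the by-level Day 15 summary twice: with all subjects, and with on-dose subjects only.
4. List the flagged subjects by actual dose.

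The cost is a few lines of SAP text and one derivation from data already collected. The on-dose summary is selected for tolerability, so it should not stand alone; showing both versions makes the difference visible.
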